4.4.2. Secondary Efficacy Variable(s)

The secondary endpoints in the study are:

- Change from baseline to weeks 2, 4, 8, 12 and 16 in the RMDQ total score
- Change from baseline to weeks 2, 4, 8, 12 and 16 in the PGA of LBP score
- Change from baseline to weeks 2, 4, 8, and 12 in the LBPI NRS score

The total score of the Roland Morris Disability Questionnaire (RMDQ) is the total number of items checked by the patient (range of 0 to 24, with lower scores indicative of better function). The Patient global assessment (PGA) of LBP is a patient assessed 5 point Likert scale of LBP (1=very well; 2=well; 3=fair; 4=poor; and 5=very poor).

4.4.3. Exploratory Variable(s)

Exploratory endpoints in the study are:

- The percentage of patients who are responders defined by 30% reduction and 50% reduction from baseline to week 16 in:
 - Average daily LBPI NRS score
 - RMDQ total score
 - PGA of LBP score
- Cumulative distribution of percent change from Baseline in average LBPI score to Week 16
- Cumulative distribution of percent change from Baseline in RMDQ total score to Week 16
- Change from baseline to weeks 2, 4, 8, 12 and 16 in the MOS-Sleep subscale score
- Change from baseline to weeks 2, 4, 8, 12 and 16 in the SF-36 subscale scores
- Change from baseline to weeks 2, 4, 8, 12 and 16 in the EQ-5D-5L visual analogue scale (VAS) and utility index scores
- Usage of rescue medication (percentage of patients who use rescue medication for LBP, number of days of usage, and weekly average amount taken during weeks 2, 4, 8 12, and 16)

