2.4. Other Objectives

Exploratory objectives of the study are:

- To evaluate the efficacy of fasinumab compared to placebo, as measured by the percentage of patients who are responders defined by 30% reduction and 50% reduction from baseline to week 16 for:
 - the average daily LBPI NRS score
 - the RMDQ total score
 - the PGA of LBP score
- To evaluate the efficacy of fasinumab compared to placebo, as measured by the change from baseline at week 16 in the Medical Outcomes Study (MOS) sleep subscale score
- To evaluate the efficacy of fasinumab compared to placebo, as measured by the change from baseline at week 16 in the Short Form (36) Health Survey (SF-36) subscale scores

- To evaluate the efficacy of fasinumab compared to placebo, as measured by the change from baseline at week 16 in the EuroQol 5 Dimensions 5 Levels Questionnaire (EQ-5D-5L)
- To evaluate the efficacy of fasinumab compared to placebo, as measured by the percentage of patients who use rescue medication for LBP at week 16
- To characterize the PK profile of fasinumab

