4.2.1. Inclusion Criteria

A patient must meet the following criteria to be eligible for inclusion in the study:

1. Male or female ≥ 35 years of age at the screening visit
2. Provide signed informed consent
3. Body mass index ≤ 39
4. Clinical diagnosis of chronic moderate to severe LBP (non-radiculopathic) for ≥ 3 months (prior to the screening visit)
 - Quebec taskforce category 1 (pain without radiation) or category 2 (pain with proximal radiation above the knee)
 - Primary pain location between 12th thoracic vertebra and lower gluteal fold
 - At both the screening and the randomization visit, an LBPI NRS score of ≥ 4 over the previous 24 hours
 - During the pre-randomization period, mean daily LBPI score of ≥ 4

- At the screening visit, PGA of LBP of fair, poor or very poor
5. History of regular analgesic medication, such as NSAIDs, COX-2 inhibitors, opioids, paracetamol/acetaminophen, or a combination thereof
 - Taking medication >4 days per week in the month prior to screening
 - Willing to discontinue current opioid pain medications starting at pre-randomization visit through the week 16 study visit
 - Willing to discontinue current NSAID pain medications (oral or topical) starting at pre-randomization visit through 16 weeks after last dose of study drug
 6. A history of inadequate pain relief or intolerance to analgesics used for chronic LBP as defined by:
 - Intolerance or inadequate pain relief from paracetamol/acetaminophen, and
 - Intolerance or inadequate pain relief from at least 1 oral NSAID, and
 - Intolerance or inadequate pain relief from at least 1 opioid, unwillingness to take opioid therapy or lack of access to opioid therapy
 7. Willing to consider TJR surgery, if necessary
 8. Willing and able to comply with clinic visits and study-related procedures
 9. Able to understand and complete study-related questionnaires

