6.3.2.3. Patient Global Assessment of Low Back Pain

The PGA of LBP is a patient-rated assessment of their current disease state on a 5-point Likert scale (1 = very well; 2 = well; 3 = fair; 4 = poor; and 5 = very poor). Patients will complete the assessment scale at the time points indicated in [Section 6.1](#).

A copy of the assessment is provided in the study reference manual.

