5.7.3. Analysis of Exploratory Variables

Responder analyses

The percentage of patients who are responders based on the variables listed in [Section 4.5.3](#) are defined by 30% reduction and 50% reduction from baseline to week 16 will be summarized by the treatment group. These response-based categorical exploratory variables will be analyzed for FAS using the Cochran-Mantel-Haenszel (CMH) test, stratified by the randomization strata.

Cumulative distribution of percent change from baseline in average daily LBPI score and RMDQ total score will be presented by treatment group. The cumulative distribution plot displays a continuous plot of the percent change from baseline on the X-axis and the percent of patients experiencing that change on the Y-axis. Different responder definitions can be identified along the cumulative distribution curve.

Continuous endpoints

All continuous exploratory variables will be analyzed for FAS using the same MMRM as described in [Section 5.7.1](#) to compare fasinumab doses with placebo without multiplicity adjustment. These models will include fixed effect terms for randomization strata, corresponding baseline value, treatment, visit, and treatment-by-visit interaction. LS mean with standard errors, LS mean difference with standard error, and its 95 % confidence interval will be provided. The graph of LS-mean +/- SE by visit will be provided. In addition, each variable, absolute value and change from baseline value will be summarized and graphed by visit.

Rescue Medication

The percentage of patients who use rescue medication between baseline and week 16 will be summarized by the treatment group. The categorical exploratory variable will be analyzed for FAS using the Cochran-Mantel-Haenszel (CMH) test, stratified by the randomization strata.

Number of days patients used rescue medication during the treatment period (Day1 to Week 2, Week 2 to Week 4, Week 4 to Week 8, Week 8 to Week 12, Week 12 to Week 16) will be summarized descriptively by treatment group. Weekly average amount of rescue medication use will be summarized descriptively by treatment group.

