6.1. Definition of Baseline for Efficacy/Safety Variables

Unless otherwise specified, the Baseline assessment for all measurements will be the latest available valid measurement taken prior to the administration of investigational product.

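### The 30%/50% reduction rule has no fixed meaning on a PGA coded 1 to 5, so the exploratory PGA responder rate should be read from a category-based rule

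*SAP*

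**What the plan says.** SAP 4.4.3 makes it an exploratory endpoint to report "The percentage of patients who are responders defined by 30% reduction and 50% reduction from baseline to week 16 in" three measures: average daily LBPI NRS, RMDQ total and PGA. Protocol 2.4 has the same rule for the same three measures ("responders defined by 30% reduction and 50% reduction from baseline to week 16 for"), and Protocol 8.3 repeats it.

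The scales differ in origin. SAP 4.4.1 gives the LBPI as 0 to 10, and SAP 4.4.2 gives the RMDQ as 0 to 24. The PGA is a "5-point Likert scale (1 = very well; 2 = well; 3 = fair; 4 = poor; and 5 = very poor") in Protocol 6.3.2.3, and SAP 4.4.2 uses the same coding.

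Three further provisions matter:

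- **Entry.** Inclusion criterion 4 in Protocol 4.2.1 requires "At the screening visit, PGA of LBP of fair, poor or very poor", that is 3, 4 or 5.
- **Baseline.** SAP 6.1 says that, unless otherwise specified, "the Baseline assessment for all measurements will be the latest available valid measurement taken prior to the administration of investigational product". Protocol Table 1 repeats the PGA on day 1, so the day 1 score is normally the baseline.
- **Analysis.** SAP 5.7.3 states: "These response-based categorical exploratory variables will be analyzed for FAS using the Cochran-Mantel-Haenszel (CMH) test, stratified by the randomization strata". The strata are baseline LBPI, duration of back pain and maximum K-L score. Baseline PGA is not one of them.

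Neither document says whether a response is 'at least' or 'more than' the stated percentage. Neither gives a category-based PGA rule.

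**The concern.** A percent reduction has a stable meaning when zero on the scale means none of the thing measured. On the PGA the best state is coded 1 and the numbers are category labels. Dividing the change by the baseline code therefore sets a bar that depends on the starting category and on the choice to number from 1 instead of 0.

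At stake is what a reader can take from a statement such as 'x% of patients had a 30% improvement in PGA'. The same one-step improvement would count for some patients and not for others. Two results shown as a lower and a higher bar could be one event for part of the sample. The LBPI and RMDQ responder rates do not have this problem in this form.

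**Working it through.** The plan states no rate or power for this endpoint, so there is no figure to reproduce. The check enumerates every possible outcome.

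**Inputs.** PGA codes 1 to 5 (SAP 4.4.2, Protocol 6.3.2.3); thresholds 30% and 50% (SAP 4.4.3). Assumption: response means at least the threshold.

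**Step 1: percent reductions.** With baseline b and week 16 score w, reduction = (b − w)/b.

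| Baseline | to 4 | to 3 | to 2 | to 1 |
|---|---|---|---|---|
| 5 | 1/5 = 20% | 2/5 = 40% | 3/5 = 60% | 4/5 = 80% |
| 4 | – | 1/4 = 25% | 2/4 = 50% | 3/4 = 75% |
| 3 | – | – | 1/3 = 33.3% | 2/3 = 66.7% |
| 2 | – | – | – | 1/2 = 50% |

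From baseline 1 no reduction is possible.

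**Step 2: categories needed.** This is the smallest whole k with k/b at or above the threshold.

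| Baseline | 30% rule | 50% rule |
|---|---|---|
| 3 (fair) | 1 | 2 |
| 4 (poor) | 2 | 2 |
| 5 (very poor) | 2 | 3 |
| 2 (well) | 1 | 1 |

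A one-category gain is a 30% response from 3 (33.3%) but not from 4 (25%) or 5 (20%). A two-category gain is a 50% response from 3 (66.7%) and 4 (50%) but not from 5 (40%). From baseline 4 the two rules are the same event. Within a single rule the bar is not different at every baseline: the 30% rule asks 2 categories from both 4 and 5, and the 50% rule asks 2 from both 3 and 4.

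**Step 3: the inequality.** Under a strict 'more than 50%', baseline 4 would need 3 categories, so the two rules separate there, and baseline 2 could never respond at 50%. The entries for baselines 3 and 5 do not change, so the dependence on baseline remains.

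**Step 4: the origin.** Code the same answers 0 to 4, so that reduction = (b − w)/(b − 1). A move from poor to fair goes from 25% (no response) to 1/3 = 33.3% (a 30% response). A move from fair to well goes from 33.3% to 1/2 = 50% (now also a 50% response). No patient's answer has changed.

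**Step 5: baseline mix.** The documents give no baseline PGA distribution, so these mixes of baselines 3/4/5 are assumptions.

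| Assumed mix, % | 30% rate if all improve 1 category | 50% rate if all improve 2 categories |
|---|---|---|
| 60/30/10 | 60% | 60 + 30 = 90% |
| 40/45/15 | 40% | 40 + 45 = 85% |
| 20/50/30 | 20% | 20 + 50 = 70% |

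Identical improvement gives different rates. The table shows only that the level of the rate shifts with mix. It says nothing about a difference between randomized arms.

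**The case against.** The strongest reply is that little rests on this endpoint and nothing in it is biased. The rule is deterministic and the same in every arm. Allocation is 1:1:1:1, so baseline PGA is balanced in expectation and the CMH comparison is valid. Change in PGA is already a secondary endpoint, analysed by MMRM with baseline PGA as a covariate and with values and changes shown by visit (SAP 5.7.2). All of this stands, and it rules out two stronger readings.

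- A reader might infer that the PGA responder rate is uninterpretable. The documents do not support that. The rate can be computed and compared between arms; what it lacks is a fixed meaning as a 30% or 50% improvement.
- A reader might infer that the rate depends on baseline mix as much as on treatment. No baseline PGA distribution and no PGA treatment effect is given, so the two cannot be compared.

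Two narrower objections also stand. The coincidence at baseline 4 rests on reading the rule as 'at least'. Baselines 1 and 2 are peripheral, because screening admits only 3 to 5; they arise only if a patient improves between screening and day 1.

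A category rule is not perfect either. Baseline 1 cannot improve, baseline 2 cannot gain two categories, and counting all one-step gains as equal is a convention on an ordinal scale. But from baselines 3, 4 and 5 both category thresholds are attainable and ask for the same number of steps.

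Lastly, the percent rule is in the protocol, and SAP section 7 reports two unblinded interim efficacy analyses. Replacing the rule outright could look post hoc. That is a reason to keep it as a supplementary result.

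**Conclusion.** The point holds as a minor one. Reading the rule as 'at least', the 30%/50% requirements are 1/2, 2/2 and 2/3 categories from baselines 3, 4 and 5. They change again if the categories are numbered from 0. The exploratory PGA responder rate therefore has no fixed meaning as a 30% or 50% improvement, and its level shifts with the baseline PGA mix. How far it shifts in this trial cannot be derived from the documents.

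The finding is confined to the PGA responder endpoint. The randomized comparison, the primary endpoint, the PGA MMRM and the LBPI and RMDQ responder rates are not affected.

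**What to change.** In SAP 4.4.3 and 5.7.3:

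- Report PGA response as improvement of at least 1 category and of at least 2 categories from baseline at week 16, and make this the interpreted PGA responder measure.
- Keep the 30% and 50% rule for LBPI and RMDQ.
- Keep the protocol's percent rule for the PGA only as a supplementary result, with 'at least' stated.
- Correct the cross-reference in 5.7.3, which points to section 4.5.3 (laboratory variables) for the responder variables; they are in 4.4.3.

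Declare the change in SAP 1.1.5, which at present records only the protocol version. It should be made and documented by blinded staff before database lock; SAP section 7 says that the study biostatistician remains blinded at subject level.

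The cost is SAP wording and one additional set of responder tables from data already collected. There are two downsides: a departure from the protocol's exploratory wording after unblinded interim analyses, and a remaining ceiling for any patients whose baseline PGA is 1 or 2.

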4.5. Safety Variables

Patient safety will be assessed through the collection of reported adverse events (AEs), clinical laboratory data, vital signs, ECG and physical exam.

Unless otherwise noted, the baseline value is defined as the last available value before the first dose of study treatment.

4.5.1. Adverse Events and Serious Adverse Events

Adverse events and serious adverse events will be collected from the time of informed consent signature and then at each visit until the end of the study. All adverse events are to be coded to a “Preferred Term (PT)” and associated primary “System Organ Class (SOC)” according to the Medical Dictionary for Regulatory Activities (the latest current available version).

An Adverse Event is any untoward medical occurrence in a patient or clinical investigation patient administered a pharmaceutical product and which does not necessarily have to have a causal relationship with this treatment.

A Serious Adverse Event is an adverse event (AE) that is classified as serious according to the criteria specified in the protocol.

Laboratory results, vital signs, or ECG abnormalities are to be recorded as AEs if they are medically relevant: symptomatic, requiring corrective therapy, leading to treatment discontinuation and/or fulfilling a seriousness criterion.

4.5.2. Adverse Events of Special Interest

Adverse events of special interest (AESI) for the fasinumab program include adjudicated arthropathy and sympathetic nervous system dysfunction, as specified in the protocol.

AESI are selected using e-CRF specific tick box on the AE page.

4.5.3. Laboratory Safety Variables

Clinical laboratory tests will consist of blood analyses (including hematology and clinical chemistry) and urinalysis. Clinical laboratory values will be converted and analyzed in international units, including associated normal ranges provided by the central laboratory. International units will be used in all listings and tables.

Clinical laboratory values in conventional (US) units will also be available in the database, with associated normal ranges (analyses can be provided upon request). Both actual test values and “change from baseline” values (defined as the post-baseline value minus the baseline value) will be used in the result summaries. Potentially clinically significant values (PCSV) ranges will be applied to the laboratory test values as applicable. The following PCSV categories will be used for the laboratory PCSV analysis tables:

- Red Blood Cells and Platelets
- White Blood Cells
- Metabolic Function
- Electrolytes
- Renal Function
- Liver Function
- Lipid Panel
- Urinalysis

4.5.4. Vital Signs

Vital sign parameters will include temperature, pulse (measured over a 1-minute period), and respiratory rate. As well as supine BP, 1 min and 3 min standing BP, supine heart rate, 1 min and 3 min heart rate which are used in the assessment of orthostatic hypotension. Both actual values and “change from baseline” values (defined as the post-baseline value minus the baseline value) will be used in the result summaries. Potentially clinically significant values (PCSV) ranges will be applied to the vital sign parameter values as applicable (see [Appendix 10.2](#) for PCSV definitions).

4.5.5. 12-Lead Electrocardiography (ECG)

12-Lead ECG parameters include P-R interval, QT interval, QTc interval including QTcF and QTcB, QRS interval, Ventricular rate and Heart rate.

QTcF and QTcB are defined as follows:

$$\text{QTcF (ms)} = \text{QT}/\text{RR}^{1/3} \quad \text{and} \quad \text{QTcB (ms)} = \text{QT}/\text{RR}^{1/2} ,$$

where QT is the uncorrected QT interval measured in ms, and RR is 60/HR with HR being the heart rate in beats per minutes. Electrocardiogram assessments will be described as normal or abnormal. Potentially clinically significant values (PCSV) ranges will be applied to the ECG parameter values as applicable (see [Appendix 10.2](#) for PCSV definitions).

4.5.6. Orthostatic Hypotension

A patient will be determined to have orthostatic hypotension if any of the following criteria are met:

- If the supine blood pressure is <160 mmHg systolic, a decrease in either the 1 min or 3 min standing systolic blood pressure of ≥ 20 mmHg or a decrease in either the 1 min or 3 min standing diastolic blood pressure of ≥ 10 mmHg from the supine systolic or diastolic blood pressure
OR
- If the supine blood pressure is ≥ 160 mmHg systolic, a decrease in either the 1 min or 3 min standing systolic blood pressure of ≥ 30 mmHg or a decrease in either the 1 min or 3 min standing diastolic blood pressure of ≥ 15 mmHg from the supine systolic or diastolic blood pressure
OR
- An increase in either 1 min or 3 min standing heart rate of ≥ 30 bpm from the supine heart rate
OR

- The patient is unable to stand for either one of the standing blood pressure measurements due to dizziness or lightheadedness

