6.3.3.6. Assessment of Orthostatic Blood Pressure

An assessment of orthostatic blood pressure will be conducted at the time points indicated in [Section 6.1](#). The assessments should be conducted as per the instructions in the study manual. A patient will be determined to have orthostatic hypotension if any of the following criteria are met:

- If the supine systolic blood pressure is <160 mm Hg, a decrease in either the 1 or 3 minute standing systolic blood pressure of ≥ 20 mm Hg, or a decrease in either the 1 or 3 minute standing diastolic blood pressure of ≥ 10 mm Hg from the supine systolic or diastolic blood pressure
OR
- If the supine systolic blood pressure is ≥ 160 mm Hg, a decrease in either the 1 or 3 minute standing systolic blood pressure of ≥ 30 mm Hg, or a decrease in either the 1 or 3 minute standing diastolic blood pressure of ≥ 15 mm Hg from the supine systolic or diastolic blood pressure
OR
- An increase in either the 1 or 3 minute standing heart rate of >30 bpm from the supine heart rate
OR
- The patient is unable to stand for the standing blood pressure measurements due to dizziness or lightheadedness

If the initial assessment for orthostatic hypotension is consistent with the above definition, the supine and standing blood pressures and/or pulse should be repeated as outlined above, up to 2 more times.

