5.8. Analysis of Safety Data

The analysis of safety and tolerability will be performed on the SAF, as defined in [Section 3.3](#). The safety analysis will be based on the reported AEs and other safety information (clinical

laboratory evaluations, vital signs, physical exam and 12-lead ECG). Thresholds for Potential Clinically Significant Values (PCSV) in laboratory variables, vital signs and ECG are defined in [Appendix 10.2](#).

The summary of safety results will be presented for each treatment group.

Period of observation: The observation period will be divided into three segments: pre-treatment, on-treatment, and follow-up period.

- The pre-treatment period is defined as the time from signing the ICF to before the first dose of study drug.
- The on-treatment period is defined as the day from first dose of study drug to 4 weeks after the last dose of SC study drug or 8 weeks after the last dose of IV study drug, whichever is later.
- The Post/Treatment follow-up period is defined as from the end of the on-treatment period+1 day to the end of study visit (week 36).

Unless otherwise noted, summaries of safety variables will use data from the on-treatment period. Listings of safety variables will include data from all periods and values occurring during the pre-treatment and follow-up period will be flagged in the listings.

Day 1 is the first day of investigational product, Day –1 is the day before, and there is no Day 0.

The time interval to detect any on-treatment event or abnormality is the on-treatment period. Data collected outside this interval will be excluded from the estimation of descriptive statistics and identification of abnormalities for laboratory evaluations, ECGs and vital signs. All post-baseline data during the interval will be using in the PCSV analysis including scheduled and unscheduled assessments.

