5.8.5. Analysis of Vital Signs

Vital signs (pulse, sitting blood pressures, orthostatic blood pressure/heart rate, and temperature) will be summarized by baseline and change from baseline to each scheduled assessment time with descriptive statistics. The graphs of mean (or median) value of some vital sign parameter vs. visit will also be plotted.

PCSV summary including orthostatic hypotension will be constructed for on-treatment period, post-treatment period and overall during the study.

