Orthostatic Hypotension	Su SBP < 160 mmHg - SBP St – Su $\leq - 20$ mmHg DBP St – Su $\leq - 10$ mmHg Su SBP ≥ 160 mmHg – SBP St – Su $\leq - 30$ mmHg DBP St – Su $\leq - 15$ mmHg	
Weight	$\geq 5\%$ increase from baseline $\geq 5\%$ decrease from baseline	FDA Feb 2007.

Parameter	Treatment Emergent PCSV	Comments
ECG		Ref.: CPMP 1997 guideline. ICH E14 2005
HR	≤ 50 bpm and decrease from baseline ≥ 20 bpm ≥ 120 bpm and increase from baseline ≥ 20 bpm	
PR	≥ 220 ms and increase from baseline ≥ 20 ms	
QRS	≥ 120 ms & < 120 ms at baseline	
QTc	Absolute values (ms) > 450 ms and baseline ≤ 450 ms > 480 ms and baseline ≤ 480 ms > 500 ms and ≤ 500 ms at baseline Increase from baseline Increase from baseline 30-60 ms Increase from baseline > 60 ms	To be applied to any kind of QT correction formula. $\Delta QTc > 60$ ms are the PCSA to be identified in individual subjects/patients listings.

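### The planned orthostatic-hypotension summary uses a blood-pressure-only rule, while the protocol and SAP 4.5.6 use four criteria and disagree on two of them

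*SAP*

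**What the plan says.** Protocol 6.3.3.6 (Assessment of Orthostatic Blood Pressure) and SAP 4.5.6 (Orthostatic Hypotension) each list four criteria, any one of which is enough. The two blood-pressure criteria are the same in both. The other two are not:

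- **Heart rate.** The protocol has "An increase in either the 1 or 3 minute standing heart rate of >30 bpm from the supine heart rate". The SAP has "An increase in either 1 min or 3 min standing heart rate of", followed by ≥30 bpm.
- **Inability to stand.** The protocol has "The patient is unable to stand for the standing blood pressure measurements due to dizziness or lightheadedness". The SAP has "The patient is unable to stand for either one of the standing blood pressure measurements due to dizziness or lightheadedness".

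For reporting, SAP 5.8.5 (Analysis of Vital Signs) states: "PCSV summary including orthostatic hypotension will be constructed for on-treatment period, post-treatment period and overall during the study". SAP 5.8 says where the PCSV rules are: "Thresholds for Potential Clinically Significant Values (PCSV) in laboratory variables, vital signs and ECG are defined in" Appendix 10.2. SAP 4.5.4 sends the vital-sign PCSV definitions to the same appendix. The orthostatic row there begins "Su SBP < 160 mmHg - SBP St – Su" and goes on only with systolic and diastolic differences.

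SAP 6.2 adds a table for repeat assessments within a visit. It says which assessment is analysed and whether the patient meets the definition, and it says frequency counts will follow that table. It refers to an orthostatic-hypotension definition without naming the section that supplies it.

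**The concern.** The SAP defines the condition by four criteria in one place and tabulates it by blood pressure alone in another. A programmer who follows 5.8.5 to Appendix 10.2 gets a different count from one who follows 4.5.6 with 6.2.

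Orthostatic assessment is one of the four routes in protocol 7.4.1.2 for monitoring sympathetic nervous system dysfunction, an adverse event of special interest. The same section requires a determination of orthostatic hypotension to lead to withholding of study drug and an adverse-event entry. Sites make that determination on the protocol's four criteria. Events of special interest reach the analysis through an eCRF tick box (SAP 4.5.2), so a rule-based summary is a useful independent check on them. A blood-pressure-only table weakens that check, and readers could not readily reconcile it with the adverse events and dosing interruptions recorded by sites.

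**Working it through.** The plan gives no figure to reproduce, so the check compares the rules and then applies each to the same hypothetical patients.

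**Step 1. The three rules side by side**

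| Criterion | Protocol 6.3.3.6 | SAP 4.5.6 | SAP Appendix 10.2 row |
|---|---|---|---|
| Fall, supine systolic <160 mmHg | ≥20 systolic or ≥10 diastolic, at 1 or 3 min | same | same cut-offs; no time point, no and/or |
| Fall, supine systolic ≥160 mmHg | ≥30 systolic or ≥15 diastolic, at 1 or 3 min | same | same cut-offs; no time point, no and/or |
| Standing heart-rate rise | >30 bpm | ≥30 bpm | absent |
| Inability to stand | the standing measurements (one or both not stated) | either one | absent |

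The heart-rate row elsewhere in Appendix 10.2 does not fill the gap. It excludes standing readings, so no PCSV criterion tests a standing rise.

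**Step 2. Hypothetical patients, supine 130/80 mmHg and heart rate 70 bpm**

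| Case | Change from supine | Protocol | SAP 4.5.6 | Appendix 10.2 |
|---|---|---|---|---|
| A. Standing 128/79, heart rate 100 | fall 2/1; 100 − 70 = +30 | No | Yes | No |
| B. Standing 128/79, heart rate 101 | fall 2/1; 101 − 70 = +31 | Yes | Yes | No |
| C. Cannot stand at all (dizzy) | none can be computed | Yes | Yes | No |
| D. 125/78, heart rate 80 at 1 min; cannot stand at 3 min | fall 5/2; +10 | No if both measurements are meant, Yes if either | Yes | No |
| E. 105/78, heart rate 80 at 1 min; cannot stand at 3 min | fall 25/2; +10 | Yes | Yes | Yes if joined by or; No if by and |
| F. 110/75, heart rate 75 at 1 min | fall 20/5; +5 | Yes | Yes | Yes if joined by or; No if by and |

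**Step 3. Reading the results**

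- A and B together separate all three rules. The two full definitions differ on heart rate only at a rise of exactly 30 bpm.
- B, C and D are lost from the appendix count. B qualifies on heart rate alone. C has no standing reading. D has a standing reading without a qualifying fall.
- E shows that inability to stand does not by itself exclude a patient. A qualifying 1-minute fall is counted if the systolic and diastolic limits are joined by or, as they are in the two full definitions.

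**Step 4. The repeat rule**

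In SAP 6.2, a first assessment that meets the definition followed by two that do not is classed as not meeting it, and the second repeat is the value analysed. Nothing in 5.8.5 or Appendix 10.2 refers to that table, and 6.2 refers to neither of them.

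**The case against.** The strongest reply is that the SAP already holds a full definition and a specific counting rule. SAP 4.5.6 is the section that defines the condition, so the unnamed definition in 6.2 most naturally means that one. Inability to stand is not a measured value, so its absence from a table of value thresholds need not mean exclusion. On this view 5.8.5 lacks only a cross-reference. This is a fair account of what was probably intended. It does not remove the conflict, because 4.5.4 and 5.8 direct vital-sign PCSV rules to Appendix 10.2 and the appendix has its own orthostatic row. It also does not explain the missing heart-rate criterion, which is a measured value.

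A second reply is that these patients are reported elsewhere. Protocol 7.4.1.2 requires an adverse-event entry, and SAP 5.8.1 tabulates treatment-emergent events. SAP 5.8.2 summarises events of special interest, and SAP 5.8.8 the Survey of Autonomic Symptoms. That stands, and it limits the consequence. A reader might infer that patients too dizzy to stand vanish from the safety report; the documents do not support that.

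A reader might also infer that unconfirmed first readings inflate the PCSV count, because SAP 5.8 puts all post-baseline data, scheduled and unscheduled, into that analysis. That sentence is general and concerns types of assessment, not repeats within a visit. The specific 6.2 table most naturally governs. What remains is that the SAP does not say so.

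**Conclusion.** The inconsistency is real and worth correcting. As written, the 5.8.5 table applies a rule that lacks two of the four criterion types in the SAP's own definition. It misses patients who qualify solely on heart rate, and those who cannot stand and have no qualifying standing reading. The protocol and SAP 4.5.6 also disagree on the heart-rate boundary and on how many standing measurements must be missed.

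The number of patients affected cannot be computed, since the documents give no rates of orthostatic hypotension, heart-rate rise or inability to stand. The boundary difference is narrow; the omissions from the appendix are the substance. The table is descriptive, so neither the efficacy analyses nor the capture of adverse events is touched.

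Two further inferences go beyond the text. The documents do not rank orthostatic hypotension as the main sign of sympathetic dysfunction, and they do not describe inability to stand as its most severe form. The conclusion rests on reading 4.5.4, 5.8 and 5.8.5 as sending the summary to the Appendix 10.2 row, which is what they say.

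**What to change.** 1. Derive one orthostatic-hypotension flag per patient and visit, using all four criterion types in SAP 4.5.6 and the repeat rule in SAP 6.2.
2. Use that flag in SAP 5.8.5 in place of the Appendix 10.2 row, and state in 6.2 that its table applies the 4.5.6 definition and governs this summary.
3. Reconcile the heart-rate boundary and the inability-to-stand wording between protocol 6.3.3.6 and SAP 4.5.6, so that one version feeds every count. Which version is clinically right is for the sponsor to settle.

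The cost is some SAP wording and one derived variable, settled before database lock. Supine and standing pressures and heart rates are already analysis variables (SAP 4.5.4). The documents do not show whether inability to stand is a coded field. If it is not, it would have to come from site records or adverse-event entries, and the SAP should name that source.
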